6.3 Description of measures taken to reduce and avoid bias

Cluster randomised trial :

- Practitioners will be randomly assigned to one of the three study groups.
- All patients of the same practitioner will be assigned to the same randomisation group.
- Randomisation will be carried out in blocks of random size.

For the duration of the study, the practitioner undertakes to offer all patients eligible for inclusion the opportunity to take part in the study.

The multicentre nature of the study will minimise the practitioner effect inherent in this type of clinical research.

The self-administered questionnaires will be given to the patient in person, and the patient will be left alone while the questionnaire is completed.

Only the analysis of the data will be unblinded. In addition, the data will be anonymised to guarantee confidentiality.

7 Duration and organisation of the research

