The aim of this study is therefore to highlight the effects of fasciatherapy on low back pain through an assessment of pain, quality of life, functionality and anxiety. It also aims to observe how fasciatherapy could contribute to the management of low back pain in the context of massage and physiotherapy.

This is a randomised cluster study with pain as the primary endpoint, involving 180 participants. The evaluation criteria include pain assessment using the Visual Analogue Scale (VAS), functional assessment using the Dallas Pain Questionnaire, quality of life evaluation with the SF-12 questionnaire, psychological assessment of anxiety using the STAI, and monitoring of medication use based on information provided by patients to the practitioner.

The practical conduct of the study is structured as follows:

- Recruitment of physiotherapists (investigators) by the FasciaFrance association and verification via their Curriculum Vitae of the investigators' inclusion criteria,
- Randomization of investigators into three groups based on the care they will provide: massage-physiotherapy care, combined massage-physiotherapy and fasciatherapy care, and fasciatherapy-only care.,
- Distribution of the investigator's brochure and observation booklet,
- Each investigator recruits their patients and adheres to the protocols outlined in the investigator's guide and observation booklet.
- Submission of anonymized ("coded") data by the investigators to the study sponsor.
- Data entry in the ACCESS database,
- Statistical analysis of the data using STATA software,
- Publication of the results.

CONTENTS

1	Gen	eral information	6	
	1.1	Title of research	6	
	1.2	Coordination and monitoring of the study - promoter	6	
	1.3	Coordinating investigator	6	
	1.4	Co-investigator - scientific collaborator - investigator - statisticians and associate partn	er 6	
	1.5	Study locations	7	
	1.6	Study timetable	7	
2	Stuc	ly rationale and scientific justification	7	
3	Aim	s of the study	9	
	3.1	Main objective	9	
	3.2	Secondary objectives	9	
4	Stuc	ly category	9	
	4.1	Search category	9	
	4.2	Justification for qualification	9	
5	Pop	Population studied / concerned		
	5.1	Inclusion criteria	9	
	5.2	Non-inclusion criteria	9	
	5.3	Procedure for early termination of research	10	
	5.4	Recruitment procedures	10	
6	Des	cription of the study	10	
	6.1	Assessment criteria	10	
	6.1.	Primary endpoint	10	
	6.1.2	2 Secondary evaluation criteria	10	
	6.2	Investigation method used	10	

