5.4 Recruitment procedures

Patients are included in the protocol by each practitioner participating in the study, as part of their usual practice. Any patient consulting a practitioner participating in the study for chronic low back pain may be included in the study. The practitioner will ensure that the inclusion and exclusion criteria are respected. At the first appointment, the patient is informed about the study and given an informed consent form. A minimum of 48 hours elapses between the consent form being handed over and the patient's consent being collected.

6 Description of the study

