7.3 Description of the general logistical organisation of the trial

Practitioners will receive an observation booklet by post. Each practitioner will include between 3 and 5 patients in the study.

The promoter is responsible for gathering all the data collected at each phase of the study and at the end of the study. They will compile the data into an Excel file and transmit it to the statistician.

- 7.4 Inclusion criteria for practitioners
 - Qualified physiotherapist,
 - Private practice,
 - Having a mixed practice combining conventional physiotherapy and fasciatherapy which is outside the scope of conventional practice,
 - Having completed at least 105 hours of training in fasciatherapy.

8 Data collected

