11.4 Feasibility of the study

- Competencies of the teams involved: All practitioners have a state diploma in massophysiotherapy and must practice fasciatherapy (with a training course of at least 105 hours).
- Recruitment possibilities: A preliminary questionnaire distributed to members of Fascia France showed that 49 practitioners were willing to participate in the study. Of these, 41 could include patients with low back pain. The total number of potential patients for inclusion ranged between 200 and 370.
- Sessions take place in the practitioner's office, which is the one the patients have contacted.

12 Financing and insurance

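### Practitioners recruit their own patients knowing their arm, and the plan does not say when offers stop or which patients fill the 3 to 5 places, so selection by arm is possible and would go unrecorded.

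*Combined protocol and SAP*

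**What the plan says.** The step list in the protocol summary, ahead of the table of contents, puts "Randomization of investigators into three groups based on the care they will provide" before recruitment. Only after the brochure and booklet have been sent out does it say "Each investigator recruits their patients and adheres to the protocols outlined in the investigator's guide and observation booklet". Section 5.4 confirms who recruits: "Patients are included in the protocol by each practitioner participating in the study, as part of their usual practice". The same practitioner checks eligibility and informs the patient. Section 6.3 fixes the allocation unit: "All patients of the same practitioner will be assigned to the same randomisation group".

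Three statements bear on which patients enter:
- Section 6.3: "the practitioner undertakes to offer all patients eligible for inclusion the opportunity to take part". This applies for as long as the study runs, and section 1.6 gives a recruitment period of 25 months (6 May 2021 to 6 June 2023).
- Section 7.3: "Each practitioner will include between 3 and 5 patients in the study".
- Section 5.4: "Any patient consulting a practitioner participating in the study for chronic low back pain may be included in the study". The wording permits inclusion; it does not require it.

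Section 11.4 reports that 41 practitioners could include patients with low back pain, and adds: "The total number of potential patients for inclusion ranged between 200 and 370".

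Section 9.1.1 plans a baseline comparison, an inclusion curve by group, and comparisons with and without adjustment for unbalanced factors.

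**The concern.** A practitioner who delivers one arm knows, before approaching anyone, what care that patient will receive. Randomising practitioners then no longer guarantees comparable patients, because who enters can depend on the arm. The usual protections are to identify patients before randomisation, to use a recruiter unaware of the arm, or to enrol consecutive patients and keep a screening log. The plan describes none of the first two and no consecutive rule. The booklet contents in section 8.1.2 include an eligibility sheet but no record of eligible patients who declined or were never approached.

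The undertaking in 6.3 therefore carries most of the weight, and it has a gap. With places limited to 3 to 5, a practitioner who sees more eligible patients than that must stop somewhere, and a range also allows stopping at three. The plan does not say where to stop or in what order places are filled. Every investigator must practise fasciatherapy (sections 7.4 and 11.4), so views about who will do well under which care are plausible even in good faith. At stake is the comparability of the arms on the primary endpoint. Adjustment can repair this only for factors that are measured.

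**Working it through.** **1. Is the arm known at recruitment?** The summary puts randomisation before recruitment, section 5.4 makes the practitioner the recruiter, and section 6.3 puts all of a practitioner's patients in one arm, which that practitioner delivers. So yes. The one sentence on blinding in 6.3 concerns the data analysis and cannot make practitioners unaware of care they give.

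**2. How far does the cap bind?** Inputs: 41 practitioners and 200 to 370 potential patients (11.4); 3 to 5 inclusions each (7.3); a target of 180 (summary; 60 per group in 9.2).
- Potential patients per practitioner: 200/41 = 4.9; 370/41 = 9.0.
- Maximum places: 41 × 5 = 205.
- Low end: 200 patients for 205 places, so the cap hardly binds on average, although individual practitioners may exceed it.
- High end: 205/370 = 55% can be included, so about 45% or more are left out.
- The target of 180 is 180/200 = 90% to 180/370 = 49% of the pool, or 180/41 = 4.39 per practitioner.

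The time window behind the 200 to 370 is not stated.

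**3. Illustration of size.** Assumptions not in the documents: all practitioners in one arm, and none in the comparator, take the 5 patients they judge most likely to respond, and that judgement correlates r = 0.2 to 0.3 with the change score. From section 9.2: SD 2 (inside 1.5 to 2.5), practitioner ICC 0.05 to 0.2, within-patient correlation 0.5 over 5 sessions, 60 per arm.

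- Shift = (mean of the top 5 of k standard normal values) × r × SD. The mean is 0 for k = 5, 0.42 for k = 7 and 0.65 for k = 9 (simulated).
- Variance factor for the five-session mean = (1 + 4 × 0.5)/5 = 0.6.
- SE of a two-arm contrast = 2 × √[(2/60) × (0.6 + 3.39 × ICC)], where 3.39 = 4.39 − 1. This gives 0.32 at ICC 0.05 and 0.41 at ICC 0.2.
- False-positive rate = Φ(shift/SE − c) + Φ(−shift/SE − c), where c is the two-sided critical value.

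| Patients taken | Shift (points) | Rate at nominal 5% | Rate at 1.7% |
|---|---|---|---|
| 5 of 5 | 0 | 5% | 1.7% |
| 5 of 7 | 0.17–0.25 | 7–12% | 3–6% |
| 5 of 9 | 0.26–0.39 | 10–23% | 4–12% |

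Both levels are shown because section 9.1.1 sets 5% for all tests, while section 9.2 sizes the comparisons at 1.7% (0.05/3). The largest shift, 0.39 points, is 39% of the 1-point lower bound for a relevant difference in 9.2.

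**The case against.** A reader might infer that sections 6.3 and 7.3 flatly contradict each other, so that no practitioner could obey both. The documents do not support that. Offering and including are different acts, and section 5.4 separates them by at least 48 hours, so offers can exceed inclusions. A practitioner who offers the study to each eligible patient in turn and stops at the fifth consent departs from 6.3 only in its duration. What is missing is a stated stopping point and order of entry. On the low feasibility figure the cap barely matters on average.

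A reader might also infer that selection by arm will happen, or that 10–23% is the expected error rate. Neither follows. The rate needs the upper pool figure, one-sided selection by every practitioner in one arm, an assumed correlation and a 5% test. Equal selection in both arms would cancel. If r is instead taken with the five-session mean, the 5-of-9 shift falls by a factor √0.6 to 0.20–0.30 points, and the rate at 5% to about 8–16%.

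Finally, the undertaking is not the only safeguard. There are an eligibility sheet (8.1.2), baseline comparison and adjustment (9.1.1), and monitoring visits that check protocol adherence (10.3). These help with enrolled patients and measured factors. None covers eligible patients who were never approached, and that part of the concern stands.

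**Conclusion.** The concern holds in a limited form. Recruitment by practitioners who know their arm is clear from the text. So is the absence of any rule on when offers stop, which patients fill the places, or how eligible patients who do not enter are counted. The plan as written permits selection by arm and would leave no trace of it. Whether it occurs cannot be read from the documents.

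The possible bias starts at zero. Under the stated assumptions it reaches 0.39 points, and the false-positive rate reaches 23% at a nominal 5% or 12% at 1.7%. These upper values rest on the assumed correlation, on one-arm-only selection and on 9 potential patients per practitioner. The procedural gap does not depend on them: known-arm recruitment, permissive inclusion and the missing log remain at any pool size. The point should be acted on, but it does not call for a redesign.

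**What to change.** In sections 6.3 and 7.3, replace the two rules with one: from a fixed start date, each practitioner offers the study to consecutive eligible patients and stops offering when the fifth consents. Add to the observation booklet an anonymous tally of eligible patients, marked included, declined or not offered. Record no individual clinical data on non-participants unless the ethics and data-protection framework allows it. Report eligible and included numbers by arm beside the inclusion curve already planned.

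If recruitment is over, report by arm whatever eligible counts can be recovered. The appointment logs named in section 10.3 may help, but nothing says they record what is needed to establish eligibility. State possible recruitment bias as a limitation.

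The cost is a protocol sentence, a one-page tally per practitioner, a few minutes of recording per eligible patient, and less freedom over whom to approach. Sample size and treatment are unchanged. The recruiter still knows the arm, so the bias is reduced and made visible rather than removed.

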Comparisons between randomisation groups will be made systematically (1) without adjustment (2) by adjusting for factors whose distribution could be unbalanced between groups.

All statistical tests will be carried out with a risk of error of the first kind α of 5%.

Part of the analyses concerning the secondary evaluation criteria should be mainly exploratory in nature. As discussed by several authors (*Bender, R.; Lange, S. Adjusting for multiple testing-When and how? J. Clin. Epidemiol. 2001, 54, 343-349; Feise, R.J. Do multiple outcome measures require p-value adjustment? BMC Med. Res. Methodol. 2002, 2, 8; Rothman, K.J. No adjustments are needed for multiple comparisons. Epidemiology 1990, 1, 43-46*), adjustment for the risk of error of 1st kind will not be proposed systematically, but on a case-by-case basis in the light of clinical and not purely statistical considerations.

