9.1.4 Method for taking into account missing, unused or invalid data

A sensitivity analysis will be carried out to study the attrition bias, i.e. the quantity (level of attrition) and nature (independence from the randomisation group) of the missing data, and to propose the most appropriate data imputation method if necessary.

9.2 Justification of the number of subjects / power analysis.

In order to evaluate the specific benefits of fasciatherapy compared with physiotherapy for chronic low back pain in terms of variation in pain before and after each of the 5 sessions considered in this protocol, the estimate of numbers is based on recruitment capacity, the time required for experimentation and simulations concerning the effect size for risks of error of 1st and 2nd kind fixed respectively at 1.7% (two-sided with correction for multiple comparisons: group receiving only conventional physiotherapy, group receiving conventional physiotherapy and fasciatherapy) and less than 20%.

Thus, if we estimate that a clinically relevant difference in pain assessment is between 1 and 2 points, for a standard deviation of the variation in pain of 1.5 to 2.5 points, we should include 30 to 40 patients for a statistical power of over 80% and an intra-individual correlation coefficient (5 sessions per subject) conventionally set at 0.5.

This proposal must be revised upwards in order to take into account the dropouts inherent in this type of protocol and the inter- and intra-practitioner variability (due to the experimental design of the cluster trial) which can be measured by the intra-class correlation coefficient and which it seems reasonable to estimate in the context of this project to be of the order of 0.05 to 0.2. It is therefore proposed to include 60 patients in each of the study groups.

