9.3 Persons responsible for the analysis

[name] [contact] [name] [contact]

Clermont-Ferrand University Hospital Clinical Research & Innovation Delegation Biometrics and Medical Economics Sector

The statistical analysis plan and its successive versions will be kept in the study file. The statistical analysis plan may be revised during the course of the study, to take into account any changes made to the protocol or any other changes in the course of the study which have an impact on the statistical analyses initially planned.

10 Quality control and assurance

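### The plan's only statement on blinding is wrong as written: it implies that care and outcome assessment are masked, and it leaves open an analysis that could readily be masked

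*Combined protocol and SAP*

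**What the plan says.** Section 6.3, which lists the measures against bias, contains the one statement on blinding that we found: "Only the analysis of the data will be unblinded". The sentence after it promises anonymised data, but the stated purpose is confidentiality, not concealment of the arm.

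The same section sets the unit of allocation: "Practitioners will be randomly assigned to one of the three study groups", and "All patients of the same practitioner will be assigned to the same randomisation group". The summary before the table of contents describes this step as "Randomization of investigators into three groups based on the care they will provide". Recruitment is by the same people (section 5.4): "Patients are included in the protocol by each practitioner participating in the study, as part of their usual practice".

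The analysis sections leave several decisions open. On multiplicity, section 9.1.1 says that adjustment will be proposed "on a case-by-case basis in the light of clinical and not purely statistical considerations". On missing data, section 9.1.4 will examine attrition and then "propose the most appropriate data imputation method if necessary". Section 9.3 adds: "The statistical analysis plan may be revised during the course of the study". The reason it gives is to reflect changes to the protocol or in the conduct of the study, and successive versions are kept on file.

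**The concern.** A blinding statement should tell the reader who knows the allocation and at what stage. This one tells the reader something that the design cannot deliver, and it gives up a safeguard that the design could have.

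What is at stake is direction. The trial compares hands-on treatments, and the outcome is the patient's own pain rating, so neither delivery nor outcome assessment is masked. That leaves the handling and analysis of the data as the stages where masking is still practical. If the statisticians see which arm is which while choosing adjustment factors, covariates, cut-offs or an imputation method, each choice can be made knowing whether it favours fasciatherapy. One of the secondary objectives (section 3.2) is worded as demonstrating a benefit of fasciatherapy, and the sponsor compiles the data file. Neither fact shows bias, but both make a masked analysis worth having.

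**Working it through.** The plan states no figure on this point, so the check is a comparison of the text.

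**Step 1. Test the literal sentence against each stage.** If only the analysis is unblinded, every other stage must be blinded.

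| Stage | What the plan provides | Blinded? |
|---|---|---|
| Practitioner | Randomised to the care delivered (summary; section 6.3) | No; cannot be |
| Recruitment | Done by the allocated practitioner (section 5.4) | No |
| Patient | Three openly different types of care (sections 7.2.1 to 7.2.3); no sham or masking described | None described |
| Primary outcome | VAS pain rated by the patient before and after each session (section 6.1.1) | None described |
| Questionnaires | Patient left alone to complete them (section 6.3) | Limits practitioner influence; does not mask the arm |
| Data entry | Double reading by investigators (section 8.3.1) | None described |
| Analysis | Declared unblinded (section 6.3) | No |

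The implied blinding fails for practitioners and recruitment, and is not provided for in any other row.

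**Step 2. Ask where masking was possible.** Under section 7.3 the sponsor compiles the data into one file and sends it to the statistician. Section 9.3 places the statisticians in a university hospital department. The transfer is therefore a natural point at which to replace arm names with codes. One complication is that the patient follow-up sheet (section 8.1.2) records a description of each session. If that description is entered in the file, it could reveal the arm even when the arm variable is coded.

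**Step 3. Separate what is fixed from what is open.**

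- Fixed (section 9.1.2): the core primary model, with group, session and their interaction as fixed effects, and patient and practitioner as random effects.
- Open (section 9.1.1): which factors are adjusted for, since this depends on apparent imbalance between groups.
- Open (section 9.1.1): whether to adjust for multiplicity. The case-by-case wording follows directly on a sentence about the secondary criteria, so it is read here as covering those.
- Open (section 9.1.3): covariates for the supplementary model, chosen from univariate results and clinical relevance.
- Open (section 9.1.3): cut-offs for categorised scores, taken from the observed distribution or from literature thresholds that are not named.
- Open (section 9.1.4): the imputation method, chosen after the missing data have been examined.

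**Step 4. Look for a lock.** Section 9.3 allows revision of the SAP during the study. No section says that a version will be finalised before the statisticians see the arms.

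**Result.** The sentence contradicts the design. As written, it also means that the open items in step 3 would be decided with the arms visible.

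**The case against.** The strongest reply is that the sentence is a translation error. An open analysis makes no sense in a list of measures against bias, whereas a statement that only the analysis is *blinded* would. The English is visibly translated elsewhere, and section 9.1.3 repeats a clause. On that reading the sponsor already intends a masked analysis. This is plausible, but the documents do not show it: no section mentions coded arms, a masked statistician or a point of unmasking. On either reading the sentence has to be replaced. What stands is that a reader should not infer a deliberate decision to open the analysis.

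The second reply is that the primary analysis is not loose. That is right for the core model. In addition, section 9.1.1 plans both unadjusted and adjusted comparisons as a matter of course, so these are not alternatives to pick between. Section 9.1.3 presents the covariate-selected model as a supplement. A reader might take the case-by-case multiplicity rule to govern the primary endpoint, but its context is the secondary criteria, and the sample size in section 9.2 uses 1.7% with a correction for multiple comparisons (0.05/3 = 0.0167). The concern is therefore mainly about adjustment, secondary and categorised outcomes, and missing data.

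The third reply is that allowing SAP revision is ordinary practice. It is, and section 9.3 gives a proper reason and keeps every version. The gap is only the missing lock before the arms are seen.

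**Conclusion.** The point holds as a defect in the blinding statement and in the order of steps around the analysis. As written, the sentence is false for practitioners, unsupported for patients, and gives up a masked analysis that the data flow would allow. It should be corrected, but it does not by itself invalidate the trial.

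Two stronger readings are tempting and are not supported.

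- A reader might want to express the problem as an inflated false-positive rate from choosing among several versions of an analysis. Such a rate would not measure the lack of blinding. Statisticians working with arms coded A, B and C see the same set of p-values as statisticians working with labelled arms. Fixing the analysis in advance removes that inflation; coding does not. What coding removes is knowledge of which choice favours which treatment, and the documents do not allow its size to be calculated.
- A reader might infer that analysis is the only stage that could have been masked. Data entry and handling could be masked too.

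The conclusion rests on the sentence meaning what it says, and on there being no separate document that provides coded arms. A masked analysis would also leave untouched any bias from open treatment and self-rated pain.

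**What to change.** Replace the sentence in section 6.3 with text along these lines:

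> Practitioners and patients are not blinded. Treatment groups will be coded A/B/C in the file sent to the statisticians, and fields that reveal the care given (e.g. session descriptions) will be withheld until the code is released. Covariates, multiplicity rule, missing-data method and cut-offs will be fixed in a dated SAP version before the code is released.

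If the sponsor's intention was a blinded analysis all along, this text records it and says how it will be done. Section 9.3 should refer to the same dated version, so that the permission to revise the SAP has a clear end point.

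The cost is small: some extra file preparation by the sponsor, which already compiles the data, and a short unmasking step once the analyses have been run on coded arms. Recoding the arm variable alone may not be enough, because other fields can reveal the care. Nothing in treatment, visits or data collection changes.
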